## Figure 3. Overall Study Design - Part 3 [if conducted]

### 3. ENDPOINTS AND BASELINE VARIABLES: DEFINITIONS AND CONVENTIONS

#### 3.1. Primary Endpoint(s)

As listed in Section 2.1 the primary endpoints in Part 1 and Part 2 are related to safety/tolerability which are described in Section 3.5. The primary endpoints in Part 3 are the plasma PK endpoints which are described in Section 3.3.

#### 3.2. Secondary Endpoint(s)

The secondary endpoints (in Part 1 and Part 2) are related to PK and are described in Section 3.3. The secondary endpoints in Part 3 are related to safety/tolerability which are described in Section 3.5.

#### 3.3. Other Endpoint(s)

##### 3.3.1. Pharmacokinetic (PK) Endpoints

The PK parameters for PF-07202954 following oral dose administration will be derived from the plasma concentration-time profiles and urine concentrations as detailed in Table 4 [following single doses in Part 1 and Part 3] and [Table 5](#) [following single and repeated doses in Part 2].

In all cases, actual PK sampling times will be used in the derivation of PK parameters. In the event that the actual sampling time is not available, the nominal time may be used if there is no evidence that the actual sampling time deviates substantially from the nominal time.

**TABLE 4. PLASMA PK PARAMETERS FOR PART 1 (SINGLE, ESCALATING DOSES) AND PART 3 (SINGLE DOSE FOOD EFFECT, IF CONDUCTED)**

Parameter	Definition	Method of Determination
AUC last	Area under the plasma concentration-time profile from time 0 to the time of the last quantifiable concentration (C last )	Linear/Log trapezoidal method
AUC inf *	Area under the plasma concentration-time profile from time 0 extrapolated to infinite time	AUC last + (C last */k el ), where C last * is the predicted plasma concentration at the last quantifiable timepoint estimated from the log-linear regression analysis
C max	Maximum observed concentration	Observed directly from data
T max	Time for C max	Observed directly from data as time of first occurrence
T lag	Lag time	Observed directly from data as time prior to the time corresponding to the first quantifiable concentration.
t 1/2 *	Terminal half-life	Log(2)/k el , where k el is the terminal phase rate constant calculated by a linear regression of the log-linear concentration-time curve: 
 
Only those data points judged to describe the terminal log-linear decline will be used in the regression.
 

CL/F*	Apparent clearance	Dose/AUC inf
V z /F*	Apparent volume of distribution	Dose/(AUC inf × k el )
CCI		

**TABLE 4. PLASMA PK PARAMETERS FOR PART 1 (SINGLE, ESCALATING DOSES) AND PART 3 (SINGLE DOSE FOOD EFFECT, IF CONDUCTED)**

Parameter	Definition	Method of Determination
CCI		

\*As data permit

**TABLE 5. PLASMA AND URINE PK PARAMETERS FOR PART 2 (REPEATED ESCALATING DOSES)**

Parameter	Day(s)	Definition	Method of Determination
Plasma			
AUC tau	1, 7, 14	Area under the plasma concentration-time profile from time 0 to time $\tau$ (tau)	Linear/Log trapezoidal method
C max	1, 7, 14	Maximum observed concentration during the dosing interval	Observed directly from data
T max	1, 7, 14	Time for C max	Observed directly from data as time of first occurrence
T lag	1, 7, 14	Lag time	Observed directly from data as time prior to the time corresponding to the first quantifiable concentration
C min	7, 14	Minimum observed concentration during the dosing interval	Observed directly from data
C av	7, 14	Average concentration	AUC tau /tau
PTR	7, 14	Peak-to-trough ratio	C max /C min
R ac,AUCtau	7, 14	Observed accumulation ratio	AUC tau (Day 7 or 14)/AUC tau (Day 1)
R ac,Cmax	7, 14	Observed accumulation ratio for C max	C max (Day 7 or 14)/C max (Day 1)
t 1/2 *	14	Terminal half-life	$\text{Log}_e(2)/k_{el}$ 
 
where kel is terminal phase rate constant calculated by a linear regression of log-linear concentration-time curve.
 
only those data points judged to describe terminal log-linear decline will be used in the regression.
 

V z /F*	14	Apparent volume of distribution	Dose/(AUC tau × k el )
CL/F	7, 14	Apparent clearance	Dose/AUC tau
CCI			
Urine			
Ae tau	14	Amount of unchanged drug recovered in urine during dosing interval	Sum of [urine concentration x urine volume] for each collection over the dosing interval
Ae tau %	14	Percent of dose recovered in urine as unchanged drug over dosing interval	100 × Ae tau /Dose
CL r	14	Renal clearance	Ae tau /AUC tau

\*As data permit

CCI

CCI

CCI

CCI

### 3.4. Baseline Variables

Baseline variables are those collected only prior to dosing. In this study baseline variables are the demographic data of age, race, weight, and body mass index which will be collected at screening and summarized by treatment in accordance with the sponsor reporting standards.

### 3.5. Safety Endpoints

The primary assessments include the standard safety endpoints listed below (see the protocol for collection days and list of parameters):

- Treatment-emergent AEs;
- Clinical laboratory tests;
- Vital signs (including BP and pulse rate);
- Cardiac conduction intervals via 12-lead ECG.

These endpoints will be summarized according to CDISC standards described in the CDISC Safety Rulebook.

### **3.5.1. Treatment Emergent Adverse Events**

Any events occurring following start of treatment (either PF-07202954 or placebo) will be counted as treatment emergent. Events that occur in a non-treatment period (i.e. follow-up) within the lag time of 28 days will be counted as treatment emergent and attributed to the previous treatment taken. Similarly, the time period for collecting AEs (“active collection period”) for each participant begins from the time the participant provides informed consent.

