1.3. Schedule of Activities

The **SoA tables** provide an overview of the protocol visits and procedures; refer to **Section 8** of the protocol for detailed information on each procedure and assessment required for compliance with the protocol. The investigator may schedule visits (unplanned visits) in addition to those listed here, in order to conduct evaluations or assessments required to protect the well-being of the participant.

SoA - TABLE A. Part 1 – Single, Escalating Doses of PF-07202954/Placebo (Cohorts 1 and 2)[refer to sub-sections in [Section 8](#) for additional details]

Visit Identifier (for list of abbreviations refer to Section 10.8)	Screen (≥ 28 days)	Periods 1-4 [dosing separated by ≥ 10 days between Periods]												Follow-up		D/C	
		-1			1			2			3			8±2 days ^a	30±2 days ^a		
		N/A	0	0.5	1	2	3	4	5	8	12	16	24	36	48	72	
Informed consent & demography	x																
Outpatient visit	x															x	
Inpatient stay at CRU		x	→	→	→	→	→	→	→	→	→	→	→	→	x		
Assessment of eligibility (& update on Day -1 in Period 1, only)	x	x															
Medical history (with update on Day -1 in Period 1, only)	x	x															
PE (plus height & body weight at Screen, only) ^b	x	x															
Review alcohol/tobacco use & contraception use	x	x													x	x	x ^c
Review prior or concomitant (non-) drug treatments	x	x													x	x	x
Supine 12-lead ECG ^d	x ^d		x	x	x	x	x	x	x	x	x	x	x	x	x ^d		x ^d
Single , supine vital signs (includes BP and pulse rate at all times)	x		x	x	x	x	x	x	x	x	x	x	x	x	x	x	x
SAE and AE monitoring	x	x	→	→	→	→	→	→	→	→	→	→	→	→	→	x	x
Continuous cardiac telemetry monitoring		x ^e	x	→	→	→	→	→	→	x							
Standard meals ^f		x	x					x	x	x	x	x	x	x	x	x	
Blinded study intervention administration			x ^g														
Blood Sampling [refer to Section 8.5 and Section 10.2] for –																	
Clinical laboratory tests (after ≥ 10 hour fast)	x	x ^h											x		x	x	x
Serum FSH [in females amenorrhoeic ≥ 12 months, only]	x																
Serum pregnancy testing [in all females]	x	x ^h												x		x	
CC1 [REDACTED]													x		x		
Pre-specified PGx and Banked Prep D1.5 (Period 1 only)			x														
Plasma PK [timepoints may be revised prior to dosing, if needed]		x	x	x	x	x	x	x	x	x	x	x	x	x	x	x	x
CC1 [REDACTED]													x		x	x	
Urine [refer to Section 10.2] for –																	
Spot sample for drug test	x	x ^h															

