Spot sample for urinalysis, UACR, UPCR (+microscopy, if needed)	x	x ^h											x		x	x	x
CC1 [REDACTED]													x				

a. Onsite Follow-up visit (8±2 days) and Follow-up telephone contact (30±2 days) to occur relative to last dose of investigational product in Period 4.

b. Complete PE at Screen *or* upon admission in Period 1; otherwise, brief PE for findings at previous PE or new/open AEs **only**, at investigator discretion.c. Confirmation of appropriate contraception use, **only**.d. **Single** ECG at screen, on-site Follow-up visit, and D/C; **triplicate** supine 12-lead ECGs at all other timepoints.e. Baseline telemetry must be captured for ≥ 2 hours while participant is awake between admission on Day -1 and 0H on Day 1 of Period 1, **only**.f. **Standard** meals served at approximate clock times matching nominal time 0H, and at 5H, and 12H relative to dosing on Day 1, while inpatient.g. Following ≥ 10 hour overnight fast, dosing at approximately 8:00AM (± 2 H) to occur **with** standard morning meal provided ~30 mins prior to dosing at 0H.h. Results must be reviewed prior to dosing on Day 1 in **each** Period.

PFIZER CONFIDENTIAL

SoA - TABLE B. Part 2 – Repeated, Escalating Doses of PF-07202954/Placebo (Cohorts 3, 4, 5, 6, 7, and optional Cohort 8)

[refer to sub-sections in Section 8 for additional details]

Protocol Activity (for list of abbreviations refer to Section 10.8)	Screen		Baseline		All at 0H (prior to dosing) unless otherwise specified												Off-Drug			Follow-up			D/C	
	-≤28	-≤2 ^a	-2	-1	1	2	3	4	5	6	7	8	9	10	11	12	13	14	15	16	17	22±2 ^b	44±2 ^b	
Study Day	-≤28	-≤2 ^a	-2	-1	1	2	3	4	5	6	7	8	9	10	11	12	13	14	15	16	17	22±2 ^b	44±2 ^b	
Informed consent & demography	x																							
Outpatient visit	x	x																				x		
Inpatient stay at CRU					x																	x		
Medical history (update)	x		x																			x		
Review alcohol/tobacco use & contraception use	x		x																		x	x		x
Review prior or concomitant (non-) drug treatments	x		x																		x			
PE (includes height at Screen) ^c	x		x																					
Body weight	x						x														x	x		
FibroScan® (after ≥4 hour fast)	x	x ^{a,j}																						
CCI																								
SAE and AE monitoring	x	x	x																		x	x	x	x
Supine 12-lead ECG ^d	x ^d																				x ^d	x ^d	x ^d	x ^d
Single , supine vital signs (BP and pulse rate)	x																				x	x		x
Standardized meals ^f				x																	x	x	x	

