4. STUDY DESIGN

4.1. Overall Design

The study is planned as a 3-part design with investigator- and participant-blinded (sponsor-open), placebo-controlled, randomized, dose-escalation in Part 1 and Part 2; and a randomized, open-label design, in Part 3 (if conducted). Participants will receive oral dose(s) of PF-07202954 and/or placebo in this study. A total of up to 88 unique participants (16 in Part 1, up to 30-40 initially in Part 2 [and potential expansion to 50-60 post formal IA and protocol amendment], and a maximum of 12 in Part 3) are planned to be randomized in this study.

In Part 1, for individual participants, the total duration of participation from the Screening visit to the telephone Follow-up visit will be 9 weeks (minimum) to 14 weeks (maximum) - as summarized in [Figure 1](#).

In Part 2, the total duration of participation in the study, for **each** participant, will be 8 weeks (minimum) to 12 weeks (maximum), including the interval from the 1st Screening visit to the telephone Follow-up visit – refer to [Figure 2](#).

In Part 3, if conducted, the total duration of participation for each participant, from the Screening to the telephone Follow-up visit, will be 5 weeks (minimum) to 10 weeks (maximum) – as outlined in [Figure 3](#).

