Given the current study is the first time PF-07202954 will be administered to humans, an escalating single oral dose design is planned with careful assessment and ongoing review of safety data and PK of PF-07202954. Part 1 is designed as a randomized, dose -escalating, cross-over, interleaving, placebo-controlled, 2-cohort, study with dosing of study intervention (PF-07202954/placebo) planned following ≥ 10 hours overnight fast, at approximately 8:00AM (± 2 hours) to occur **with** standard morning meal provided ~ 30 mins

prior to dosing at 0H. By design, at each dose level, 6 participants are planned to receive PF-07202954 and 2 participants are planned to receive placebo with all participants at the end of Part 1 having received 1 dose of placebo and up to 3 *unique* doses of PF-07202954. The rationale for selection of the starting (ie, first) dose level in Part 1 is outlined in [Section 4.3.3](#). In addition, the highest anticipated steady-state AUC₂₄ and C_{max} for PF-07202954 in Part 1 will *not* exceed the pre-identified stopping exposure limit determined based on nonclinical toxicity study (refer to [Section 6.6.1](#)) *nor* exceed the highest feasible total daily dose of 2000 mg.

The design of Part 1 permits both a within and between participant assessment of safety/tolerability and dose-response for PK and exploration of effect on plasma PCSK9. Furthermore, to permit an unbiased assessment of safety, the administration of active versus placebo in each Period will be double-blinded to both site staff (except those involved in preparation of doses) as well as the participants. However, to permit real-time review of the safety and PK data, the sponsor will be unblinded, although measures to limit degree of unblinding will be exercised – refer to [Section 9.5](#) for details. In light of the findings in the 6 week toxicity studies in rats and monkeys, the safety assessments envisioned in this study administrating investigational product for the first time to humans are outlined in [Section 8.2](#).

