For a given participant, dosing will be separated by **≥10 days**, with this planned dosing interval deemed sufficient based on the predicted PF-07202954 effective half-life of approximately 8 hours. In addition, this interval accounts for the required time for review of the safety, tolerability, and PK data from each dosing period before making a decision on the subsequent PF-07202954 dose to be evaluated. The planned doses in the escalation sequence (refer to [Table 3](#)) may be modified or repeated, as guided by emerging safety and PK data but will follow the dose-escalation rules defined in [Section 6.6.1](#). The data from participants as they receive placebo will be pooled and compared to data from each active dose to determine the next escalating dose of PF-07202954. The assessment of the full range of doses will require the planned 8 Periods of dosing (4 Periods per participant). In the event that additional dose-escalation is no longer warranted (eg, maximum tolerated dose identified, clear evidence of plateau in plasma PK based on observed data with at least 2 dose-levels), the additional periods in this 4-Period, cross-over design may be used to repeat a previously administered dose, study a lower and/or intermediate dose, and/or undertake an exploratory assessment of plasma PK with dosing following an overnight fast of **≥10 hours** *or* dosing following a high fat/high caloric morning meal (compared to dosing following a standard morning meal in previous Periods within the same cohort) to explore any potential food effect. And pending observed plasma PK data from Part 1, this study may also conduct Part 3 – refer to [Section 4.2.4](#) – to compare plasma PK following dosing in the fasted state (Reference) to dosing with a high-fat/high-caloric morning meal (Test).

4.2.3. Rationale for Part 2

[figure not shown]

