8.3.1. Time Period and Frequency for Collecting AE and SAE Information

The time period for actively eliciting and collecting AEs and SAEs (“active collection period”) for each participant begins from the time the participant provides informed consent, which is obtained before the participant’s participation in the study (ie, before undergoing any study-related procedure and/or receiving study intervention), through and including ***a minimum of 28 calendar days***, except as indicated below, after the last administration of the study intervention.

Follow-up by the investigator continues throughout and after the active collection period and until the AE or SAE or its sequelae resolve or stabilize at a level acceptable to the investigator and Pfizer concurs with that assessment.

For participants who are screen failures, the active collection period ends when screen failure status is determined.

If the participant withdraws from the study and also withdraws consent for the collection of future information, the active collection period ends when consent is withdrawn.

If a participant definitively discontinues or temporarily discontinues study intervention because of an AE or SAE, the AE or SAE must be recorded on the CRF and the SAE reported using the CT SAE Report Form.

Investigators are not obligated to actively seek AE or SAE after the participant has concluded study participation. However, if the investigator learns of any SAE, including a death, at any time after a participant has completed the study, and he/she considers the event to be reasonably related to the study intervention, the investigator must promptly report the SAE to Pfizer using the CT SAE Report Form.

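### In Part 1 the AE attribution rule gives Period 4 treatments a 28-day window against about 10 to 12.7 days in Periods 1-3, so crude AE incidence by treatment is not comparable

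*SAP*

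**What the plan says.** SAP 3.5.1 counts any event after the start of treatment as treatment emergent. Events in a non-treatment period, for which follow-up is the only example given, are treated as follows: those "within the lag time of 28 days will be counted as treatment emergent and attributed to the previous treatment taken".

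The Part 1 schedule (Protocol 1.3, SoA Table A) reads "Periods 1-4 [dosing separated by ≥ 10 days between Periods", with the final "Follow-up telephone contact (30±2 days) to occur relative to last dose of investigational product in Period 4". Protocol 8.3.1 keeps active AE collection open for "a minimum of 28 calendar days" after the last administration. The primary endpoint (Table 2 in both documents) has the same shape: at least 10 days in each period, and up to Day 30±2 after the last dose.

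Protocol 4.2.2 states that at each dose level "6 participants are planned to receive PF-07202954 and 2 participants are planned to receive placebo". Table 5 of the Protocol ties dose number to period: Doses 1 and 2 in Period 1, 3 and 4 in Period 2, 5 and 6 in Period 3, 7 and 8 in Period 4. Each sequence has one placebo period. Placebo data are pooled and compared with each active dose (Protocol 4.2.2).

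SAP 6.6 plans no formal analysis of standard safety data, and SAP 6.6.1 leaves TEAE reporting to sponsor standards. Neither mentions a common window or an adjustment for person-time. For vital signs and ECG, by contrast, SAP 3.5.3 and 3.5.4 confine the Part 1 maximum change to the period concerned.

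**The concern.** Once a participant takes the next dose, that dose becomes the previous treatment, so the earlier treatment stops collecting events. Only the Period 4 treatment has no successor. Length of observation therefore depends on period, and active dose number depends on period too.

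AEs are the first-listed primary endpoint of Part 1. In a crude by-treatment table, a background event such as a cold or a headache has more time to be charged to a Period 4 treatment than to an earlier one. Pooled placebo lies in between, so Doses 1-6 can look better tolerated than placebo for no pharmacological reason, and the Period 4 active treatment can look worse. The optional interim analysis on the Part 2 exposure limit would use Part 1 safety data analysed by the methods in this SAP (SAP 7.2), so the table may inform more than the final report.

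**Working it through.** **Inputs.** Dose spacing of at least 10 days and telephone follow-up at 30±2 days (SoA Table A); 28-day lag (SAP 3.5.1); 2 participants per sequence, 8 sequences (Protocol Table 5). Participation "from the Screening visit to the telephone Follow-up visit will be 9 weeks (minimum) to 14 weeks (maximum" (Protocol 4.1). The documents give no background AE rate, so every rate below is an assumption shown over a range.

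**1. The plan's own duration.** Duration = screening + 3 × spacing + follow-up.
- Minimum: with 5 days of screening (assumed), 5 + 3×10 + 28 = 63 days = 9.0 weeks, as stated.
- Maximum: 14 weeks = 98 days. If screening and follow-up are also at their longest (28 and 32 days), mean spacing = (98 − 28 − 32)/3 = 12.7 days.

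The working range for spacing is therefore 10 to 12.7 days.

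**2. Attribution windows.** Placebo falls in Period 4 only in sequences 4 and 8, so in 4 of 16 administrations.

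| Spacing | Doses 1-6 | Pooled placebo | Doses 7-8 |
|---|---|---|---|
| 10 days | 10 | (12×10 + 4×28)/16 = 14.5 | 28 |
| 12.7 days | 12.7 | (12×12.67 + 4×28)/16 = 16.5 | 28 |

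**3. Expected event counts relative to placebo, inert drug, constant rate.**
- 10-day spacing: 10/14.5 = 0.69 and 28/14.5 = 1.93.
- 12.7-day spacing: 12.67/16.5 = 0.77 and 28/16.5 = 1.70.

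Put the other way, one of Doses 1-6 with a true rate 14.5/10 = 1.45 times that of placebo (16.5/12.67 = 1.30 at the longer spacing) would show no excess.

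**4. Share of participants with any AE, inert drug, 10-day spacing.** With p the risk per 10 days, the share is p for Doses 1-6, 1 − (1 − p)^2.8 for Period 4, and 0.75 × the first + 0.25 × the second for placebo. The last column is the exact binomial probability that a given Period 4 dose shows more participants with an AE than a given earlier dose, with 6 in each.

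| p (assumed) | Doses 1-6 | Placebo | Doses 7-8 | P(Period 4 dose shows more) |
|---|---|---|---|---|
| 5% | 5.0% | 7.1% | 13.4% | 47% |
| 10% | 10.0% | 13.9% | 25.5% | 63% |
| 20% | 20.0% | 26.6% | 46.5% | 76% |
| 30% | 30.0% | 38.3% | 63.2% | 82% |

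**5. If reporting thins after discharge.** Let the daily rate after the first 4 days be a fraction r of the inpatient rate (assumed). Expected counts are proportional to 4 + 6r (Doses 1-6), 4 + 24r (Period 4) and 4 + 10.5r (placebo: 0.75 and 0.25 of the two).

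| r | Doses 1-6 / placebo | Period 4 / placebo | Period 4 / Doses 1-6 |
|---|---|---|---|
| 1 | 0.69 | 1.93 | 2.8 |
| 0.5 | 7/9.25 = 0.76 | 16/9.25 = 1.73 | 2.3 |
| 0.25 | 5.5/6.625 = 0.83 | 10/6.625 = 1.51 | 1.8 |
| 0.1 | 4.6/5.05 = 0.91 | 6.4/5.05 = 1.27 | 1.4 |

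**6. With a common 10-day window.** Every treatment has 10 days and every ratio is 1.0 for an inert drug. At p = 10%, each dose expects 0.6 of 6 participants with an AE, instead of 0.6 for Doses 1-6 and 1.53 for Doses 7-8.

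**The case against.** A reader might infer that the long window always falls on the highest doses, so that the table will show a dose trend even for an inert drug. The documents do not support either step.

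- **Not always the top doses.** Protocol 4.2.2 and the Table 5 footnotes allow Period 4 to be a repeat, a lower or intermediate dose, or a fasted or high-fat dosing. Protocol Table 3 lists only six doses. Given in order, the highest (1000 mg, projected AUC24 18,000 ng•h/mL) is Dose 6, in Period 3 with the short window. On proportional projection the 18,400 limit is reached at 18,400/18,000 × 1000 = 1022 mg, so Doses 7 and 8 could not be materially higher unless observed PK differs. On the other side, Protocol 4.2.2 also says the full dose range needs all eight periods, so the top-dose case is foreseen but not fixed.
- **Not a trend.** The pattern for an inert drug is flat over Doses 1-6 with a step in Period 4, and with 6 per dose it may not appear.

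Further points have weight. Safety summaries are descriptive. Each AE gets its own causality assessment, which considers timing. Escalation can proceed on data to 24 hours post dose (Protocol 6.6.1), so this table does not drive it. Sponsor reporting standards, which are not in the documents, may handle the windows. That an earlier window closes at the next dose is inferred from the wording; SAP 3.5.1 does not mention washout. The unequal follow-up is also built into the protocol's primary endpoint.

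These points limit the consequence but leave the comparison unequal. Whatever is given in Period 4 is inflated, including a food condition set against the standard meal. The flattering of Doses 1-6 against placebo does not depend on which active treatment Period 4 holds.

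**Conclusion.** The concern holds in a limited form. As written, the rule makes Part 1 crude AE incidence by treatment non-comparable across periods: 28 days against about 10 to 12.7, with pooled placebo at 14.5 to 16.5. For an inert drug this implies relative counts of 0.69 to 0.77 for Doses 1-6 and 1.70 to 1.93 for the Period 4 active treatment.

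These figures assume that earlier windows close at the next dose, that spacing is 10 to 12.7 days, that all periods are completed, and that background risk is constant. If reporting thins after Day 4 to a tenth of the inpatient level, they move to 0.91 and 1.27 at 10-day spacing. AEs at the top doses are overstated only if escalation uses all eight slots. With no formal test and no escalation rule resting on the table, this is a worthwhile, inexpensive improvement and does not invalidate the plan.

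**What to change.** In SAP 3.5.1, state that Part 1 events, including those in washout, are attributed to the most recent dose. In SAP 6.6.1:

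- Add a Part 1 by-treatment TEAE table with one window for every treatment, from dosing to 10 days post dose or to the next dose if earlier, and use it to compare each dose with pooled placebo.
- Show events after Day 10 in a separate row or listing.
- Keep the all-events TEAE table to Day 28, so the protocol's primary endpoint is unchanged.

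The protocol's own reasoning supports ten days as a comparison window: the spacing was chosen "with this planned dosing interval deemed sufficient based on the predicted PF-07202954 effective half-life of approximately 8 hours", and 240/8 = 30 such half-lives. A rate per participant-day is an acceptable alternative; it removes the window difference if background risk is constant.

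The cost is one date cut-off and one extra table, with slightly fewer events in the comparative display. No event is dropped. Part 2 is parallel, and in Part 3 the order of conditions is randomised so neither is tied to the last period; the change is aimed at Part 1 only.
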